1.3 DETERMINATION OF SAMPLE SIZE

1.3.1 Original sample size

At time of initial protocol, calculations to determine the sample size of 1635 patients per treatment group are based on superiority testing of the primary efficacy variable of the proportion of patients reaching individualized HbA1c target at Month 6 without a documented symptomatic (BG \leq 70 mg/dL) or severe hypoglycemic event at any time of day from baseline to Month 6, with the following assumptions:

- Individualized HbA1c target attainment per HEDIS criteria of $<8\%$ if older or presence of medical comorbidities, or otherwise $<7\%$,
- An absolute difference of 5.5% in favor of Toujeo in patients assigned a target HbA1c $<7\%$, assuming a 30.1% rate in the Toujeo arm, based on data from the EDITION 3 study,
- An absolute difference of 5.4% in favor of Toujeo in patients assigned a target HbA1c $<8\%$, assuming a 55.8% rate in the Toujeo arm, based on data from the EDITION 3 study,
- An absolute overall (weighted average) difference of 5.5% in favor of Toujeo for all patients combined, assuming that 70% of the study patients would have a target HbA1c $<7\%$, and 30% would have a target HbA1c $<8\%$, based on data from a commercially available database,
- A maximum overall response rate of 33% in the comparator basal insulins arm,
- A 2-sided chi-squared test at the 5% significance level, with 90% power,
- All patients will be eligible for the primary endpoint analysis.

The assumptions are based on data from the EDITION program.

As a logistic regression model will be used for the primary analysis of the composite endpoint of individualized HbA1c target attainment without hypoglycemia, it is anticipated that the power will be higher due to reduced estimate variability compared with the chi-square test. Calculations were made using nQuery Advisor 6.01.

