For documented hypoglycemia, if a patient drops out from the study prior to 6 months and no documented hypoglycemia is entered into the CRF during the first 6-month treatment period, the patient status with regard to documented hypoglycemia (presence or absence of hypoglycemia) will be considered as missing. Similarly, if a patient drops out from the study prior to 12 months and no documented hypoglycemia is entered during the 12-month treatment period, the patient's documented hypoglycemia status will be considered missing. If a patient has a documented hypoglycemia event within the time frame, then this subject will be considered as a subject with documented hypoglycemia, no matter it is a completer or early withdrawal.

Missing data will be imputed 100 times to generate 100 complete data sets with the MI with Markov Chain Monte Carlo (MCMC) method in SAS procedure in two steps.

- Step 1: Six-month HbA1c value will be imputed using the regression method with stratification factors and treatment. For each simulation leading to imputed HbA1c values outside of 3.5% to 16%, another value will be redrawn for imputation.
- Step 2: If the 6-month documented (BG \leq 70 mg/dL) hypoglycemia status is missing, after Step 1, HbA1c is imputed, 6-month documented (BG \leq 70 mg/dL) hypoglycemia status will be subsequently imputed using a logistic regression method with 6-month HbA1c, stratification factors, and treatment.

For each of the 100 imputed datasets, the composite endpoint will be constructed and compared between treatment groups using the same logistic regression model as specified above in the primary efficacy endpoint analysis. The estimates from the 100 fitted models will be combined to provide an overall estimate with corresponding confidence intervals (CI). The difference between treatments and the corresponding CI will be presented. The imputed values of HbA1c will also be used in the analysis of HbA1c change as continuous variable (secondary efficacy endpoint).

- **Sensitivity analysis of primary efficacy endpoint with tipping point analysis.**

Robustness of the primary analysis results to departure from the MAR assumption will be explored in the ITT population using tipping-point analysis based on the pattern mixture model approach.

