Estimations will be performed using the same multiple imputation approach as described previously. In each treatment arm, a penalty δ will be added to the imputed values ($\delta = 0$ corresponds to the MAR assumption) in the HbA1c multiple imputation step.

The documented hypoglycemia status will be imputed as described previously following the HbA1c imputation with various δ .

To investigate how the conclusions for the composite endpoint depend on the adopted values δ , the testing will be repeated over a range of plausible values for the pairs (δ_{Toujeo} , $\delta_{\text{std_care_basal_insulin}}$). The δ values range from -1 to 1 by 0.1, in each treatment group. Results will then be summarized using graphs.

The smallest value of δ_{Toujeo} for a value of $\delta_{\text{std_care_basal_insulin}}$ equal to 0 which will statistically reverse the conclusion for the composite primary endpoint will be assessed and interpreted from its clinical plausibility.

- **Sensitivity analysis excluding patient data from sites at which research activities were terminated due to non-compliance.**

A sensitivity analysis using the same method as for the primary efficacy analysis will be performed excluding patient data from sites at which research activities were terminated due to ongoing non-compliance with the clinical protocol and violations of GCP.

Sites [REDACTED] and site [REDACTED] are the two concerned. They will be excluded for a sensitivity analysis at 6 months.

Subgroup Identification based on Differential Effect Search

If superiority of Toujeo with respect to standard-of-care basal insulin is not shown in the primary efficacy analysis, an exploratory analysis will be conducted to identify potential subgroups of patients with enhanced treatment effect of Toujeo versus standard of care (Lantus or Levemir) basal insulin.

A procedure based on Subgroup Identification based on Differential Effect Search (6) will be employed to identify such subgroups of potential responders.

The outcome variable used in the SIDES method is the primary endpoint of the study which is the proportion of patients with individualized HbA1c target at 6 months, without any documented symptomatic or severe hypoglycemia.

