2.5.2 Data handling conventions for secondary efficacy variables

Fasting condition

FPG measurement not collecting in fasting condition will not be used in the analyses.

Invalid laboratory data

HbA1c or FPG measurements flagged as invalid by the laboratory will not be used in the analyses.

Treatment persistence/switch

A switch is defined by:

- A switch from Toujeo IMP to any commercial “standard of care” basal insulin or,
- A switch from “Lantus or Levemir” IMP basal insulin to commercial Toujeo.

Change in “standard of care” basal insulin to another basal insulin not being considered as a “switch”.

Remain on assigned therapy is defined by,

- Neither permanently withdraw,
- Nor switch:
 - From IMP Toujeo to Lantus or Levemir insulin,
 - Or from “standard of care” basal insulin to commercial Toujeo,
- Assigned therapy refers to the treatment allocated by IRT: Toujeo or Lantus/Levemir,
- Commercial Toujeo not being allowed in both treatment arms.

Persistence is defined by,

- Remained on assigned therapy.

HbA1c target and severe and or symptomatic hypoglycemia

HbA1c target missing data handling,

- Patients with missing HbA1c data at respectively Month 6 and Month 12 will be regarded as not having reached the HbA1c target (ie, as failure) at each given time-point.

Symptomatic hypoglycemia target missing data handling

In case of at least one symptomatic event with glycemic value missing it will be considered that the patients experiences at least:

- One document symptomatic hypoglycemia (BG ≤ 70 mg/dL [≤ 3.9 mmol/L]) and,
- One document symptomatic hypoglycemia (BG < 54 mg/dL [< 3.0 mmol/L]).

In case of at least one symptomatic event with timing missing it will be considered that the patients experiences at least:

- One symptomatic hypoglycemia event occurring at any time of the day and,
- One nocturnal symptomatic hypoglycemia event.

Composite endpoints missing data handling

- For each cases presented above regarding missing HbA1c values the patient will be considered as failure for each composite endpoint of the corresponding randomized period.
- For each case presented above regarding missing hypoglycemia event information the patient will be regarded as failure for each related composite endpoint.
- In case of premature end of study during the 6 month randomized period the patient will be considered as failure for each composite endpoint relative to the 6-month and the 12 month period.

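### The tipping-point analysis shifts imputed HbA1c but never imputed hypoglycemia, so its tipping value tests only one of the two imputed components of the composite

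*SAP*

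**What the plan says.** SAP 2.4.4.1 states the aim: "Robustness of the primary analysis results to departure from the MAR assumption will be explored in the ITT population using tipping-point analysis". The method builds on the two-step multiple imputation described just before it. Step 1 imputes 6-month HbA1c. In Step 2, where status is missing, "hypoglycemia status will be subsequently imputed using a logistic regression method with 6-month HbA1c, stratification factors, and treatment". Status counts as missing only "if a patient drops out from the study prior to 6 months and no documented hypoglycemia is entered into the CRF" during the first six months; anyone with a recorded event keeps it.

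For the tipping point, a delta "will be added to the imputed values" in the HbA1c step. Delta "values range from -1 to 1 by 0.1, in each treatment group"; no unit is printed, and I read it as HbA1c percentage points. Then: "The documented hypoglycemia status will be imputed as described previously following the HbA1c imputation with various" delta. Results are graphed over pairs of deltas. The headline value is the smallest Toujeo delta, with the comparator delta at 0, that reverses the conclusion for the composite.

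No delta, odds multiplier or other departure from MAR is specified for hypoglycemia. The SAP does not say explicitly whether Step 2 receives the shifted HbA1c, although that is the natural reading.

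**The concern.** A patient succeeds only by reaching the HbA1c target and having no documented symptomatic or severe hypoglycemia. Both components can be missing and both are imputed, but only one is stressed.

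The untested component is the more exposed one. HbA1c is measured in a central laboratory blinded to treatment (Protocol 8.3). Hypoglycemia is reported by patients through an e-diary or paper form in an open-label trial and entered by the site (Protocol 9.2.2.2.3). The flow chart (Protocol 1.2) has no scheduled on-site visit between Day 1 and Day 180, and sites are only encouraged to review events near Days 45 and 90 (Protocol 10.1.1.6). A dropout whose events were never entered is therefore treated as missing and imputed under MAR. Protocol section 4 also places the expected advantage in hypoglycemia: earlier phase 3 studies found Toujeo non-inferior on HbA1c, with fewer patients having nocturnal events.

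At stake is the robustness statement. A reader would take the tipping value as applying to the composite, when it bounds departures in HbA1c alone.

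**Working it through.** **1. Check of the design inputs.** The plan gives no tipping figure, so I checked its sample size first. With 33% ("A maximum overall response rate of 33% in the comparator basal insulins arm") and 38.5% (33% + 5.5 points), two-sided alpha 0.05 and 90% power:

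n = [1.960·√(2·0.3575·0.6425) + 1.282·√(0.385·0.615 + 0.33·0.67)]² / 0.055² = 1594 per arm, or 1630 with continuity correction, against the stated 1635.

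**2. How far the Toujeo arm can fall.** Use 1662 per arm (SAP 1.3.2) and final alpha 0.046 (SAP 2.4.4.1), critical value 1.995, comparator at 33%, and ignore between-imputation variance.

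- At delta 0: Z = 0.055 / √(2·0.3575·0.6425/1662) = 0.055/0.01663 = 3.31.
- Z falls to 1.995 when the Toujeo rate is about 36.3%.
- If 20% of Toujeo patients are imputed with success rate S, then 0.8·0.385 + 0.2·S = 0.363, so S ≈ 27.5%. Success among imputed patients can fall about 11 points, from 38.5%, before the conclusion reverses.

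**3. Success among imputed patients.** With H normal and p the hypoglycemia probability,

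S = 0.7·E[1(H+δ<7)(1−p)] + 0.3·E[1(H+δ<8)(1−p)],

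logit p = a + ln(OR)·HbA1c + θ.

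The 70/30 target mix is from SAP 1.3.1. Assumed, and not in the documents: SD of H 1.1; hypoglycemia rate 20% or 35%; OR per +1% HbA1c from 0.6 to 1.25; fraction imputed 10% to 30%; all imputed patients missing both components. The mean of H and a are set so that S = 38.5% at δ = 0, θ = 0. The plan as written has θ = 0 always.

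**4. Tipping delta, 20% of Toujeo patients imputed.**

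| Hypoglycemia rate | OR per +1% HbA1c | As planned (shifted HbA1c in Step 2) | Unshifted HbA1c in Step 2 | As planned, plus Toujeo hypoglycemia odds doubled (θ = ln 2) |
|---|---|---|---|---|
| 20% | 1.25 | 0.41 | 0.43 | 0.23 |
| 20% | 1.0 | 0.43 | 0.43 | 0.21 |
| 20% | 0.75 | 0.46 | 0.43 | 0.20 |
| 20% | 0.6 | 0.49 | 0.42 | 0.20 |
| 35% | 1.25 | 0.47 | 0.51 | 0.10 |
| 35% | 1.0 | 0.51 | 0.51 | 0.07 |
| 35% | 0.75 | 0.59 | 0.51 | 0.03 |
| 35% | 0.6 | 0.66 | 0.50 | 0.03 |

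With 10% imputed, the planned value runs from 0.90 to beyond the +1 limit of the grid, and doubling the odds gives 0.73 to 0.96. With 30% imputed, the planned value is 0.27 to 0.46; doubling leaves at most 0.07 and in several cases reverses the conclusion at delta 0.

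A cruder set of inputs, not calibrated to 38.5% (mean 7.45, SD 1.0, 30% hypoglycemia, OR 0.75), gives the same order of effect: doubling the odds cuts S from 28.6% to 21.2%, about 7 points.

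**5. Side effect of feeding shifted HbA1c into Step 2.** The share of the HbA1c penalty recovered is (S planned − S unshifted)/(38.5% − S unshifted). For example, at 35% hypoglycemia, OR 0.6, δ = 0.3: (33.8 − 31.8)/(38.5 − 31.8) ≈ 30%, the largest case. Over δ = 0.3 to 1.0:

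| OR per +1% HbA1c | 20% hypoglycemia | 35% hypoglycemia |
|---|---|---|
| 0.6 | 9 to 15% | 19 to 30% |
| 0.75 | 5 to 8% | 10 to 17% |
| 1.0 | 0% | 0% |
| 1.25 | −2 to −4% (penalty amplified) | −6 to −10% (penalty amplified) |

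**The case against.** **Much hypoglycemia-related dropout is already captured.** A recorded event counts whether or not the patient completes (SAP 2.4.4.1). A symptomatic event with no glucose value is counted as documented (SAP 2.5.2). Patients who stop study insulin are asked to keep reporting and to return at Day 180 (Protocol 10.3.3). This stands and narrows the point to study dropouts with no event in the CRF. A reader might infer that leaving because of hypoglycemia is wholly untested, or is the likeliest departure from MAR; the documents support neither.

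**The primary result does not rest on MAR.** Missing HbA1c is failure, and "In case of premature end of study during the 6 month randomized period the patient will be considered as failure for each composite endpoint" (SAP 2.5.2). True, but the rule is the same in both arms and does not test a difference between arms in unrecorded events.

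**Step 2 is already pessimistic.** It ignores event-free time before dropout. Assume a constant hazard, 30% six-month risk and uniform dropout times. The residual risk of a dropout with no event is then about 17%, while the model, fitted with dropouts who had events but without those who had none, imputes 31 to 33% at 10 to 20% dropout. That is an odds ratio of about 2.3 to 2.4. This stands as a caution: doubling the odds on top of Step 2 is a harsh scenario. But the pessimism applies to both arms, whereas a tipping analysis concerns a differential departure.

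**Using shifted HbA1c is legitimate.** It keeps the fitted relation between the components. I agree; it is a modelling choice and not an error.

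**Conclusion.** The point holds for the hypoglycemia component. The analysis applies a departure from MAR to imputed HbA1c only, so its tipping value does not cover differential unrecorded hypoglycemia among open-label study dropouts with no event in the CRF. Under the assumed inputs the omission can matter: with 20% imputed, doubling the Toujeo odds lowers the tipping delta from 0.41–0.66 to 0.03–0.23. Those figures rest on assumed HbA1c spread, hypoglycemia rate, odds ratio and fraction missing. They illustrate scale and do not predict the trial's result.

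A reader might go further and infer that every HbA1c penalty is partly handed back as less imputed hypoglycemia. The documents do not support that. It requires a negative fitted association between HbA1c and hypoglycemia, and neither its sign nor its size is given. With no association nothing is recovered, and with a positive one the penalty grows. Patients pushed above target fail whatever their hypoglycemia draw. In the cases computed at most about 30% is recovered and the penalty is never reversed. At OR 0.75 the tipping delta moves from 0.43 to 0.46, or from 0.51 to 0.59, less than one 0.1 grid step; only the most extreme case (OR 0.6, 35%) exceeds a step, at 0.50 to 0.66. This is a modest, conditional side effect.

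Nothing here undermines the primary analysis. It is a gap in one sensitivity analysis.

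**What to change.** Keep the HbA1c delta grid. Add a second sensitivity parameter to Step 2: a shift on the log-odds of imputed hypoglycemia by arm, for example odds ratios 1, 1.5, 2 and 3 for Toujeo with the comparator at 1. Report the two-way tipping frontier (HbA1c delta by hypoglycemia odds ratio), and give the number of patients per arm whose hypoglycemia status is imputed, so that the reader can judge how much the second axis matters.

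State whether Step 2 uses the shifted or the unshifted HbA1c. Either is acceptable once stated, and saying so removes a programming ambiguity.

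The cost is SAP wording, one more loop over the imputations, and a two-dimensional display in place of a single headline value. No new data are needed, and the primary analysis, alpha and sample size stay as they are.

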1.2 OBJECTIVES

1.2.1 Primary objectives

The primary objective of this study is to demonstrate clinical benefit of Toujeo in achieving individualized HEDIS HbA1c targets as defined below at 6 months without documented symptomatic ($BG \leq 70$ mg/dL) or severe hypoglycemia at any time of day from baseline to 6 months in uncontrolled insulin naive patients with type 2 diabetes initiating basal insulin therapy in a real world setting.

The individualized HEDIS HbA1c targets for this study are:

- HbA1c $<8\%$ if the patient is ≥ 65 years,
- HbA1c $<8\%$ if the patient is <65 years, and with evidence of any of these diseases/conditions:
 - Coronary artery bypass surgery or Percutaneous coronary intervention,
 - Ischemic vascular disease,
 - Thoracic aortic aneurysm,
 - Chronic heart failure,
 - Prior myocardial infarction,
 - Chronic renal failure/End stage renal disease,
 - Dementia,
 - Blindness,
 - Lower extremity amputation,
- HbA1c $<7\%$ if the patient is <65 years, and without evidence of any of these diseases/conditions listed above.

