1.5 MODIFICATIONS TO THE STATISTICAL SECTION OF THE PROTOCOL

In the protocol (1) Section 11.4.2, Analyses of efficacy endpoints, defines the analysis of HbA1c endpoints (change from baseline to 6 months) and self-reported satisfaction score using a mixed-effect model with repeated measures (MMRM) approach under the missing at random (MAR) framework, using an adequate contrast at Month 6. Since at the time of the 6 month database lock, only baseline and 6 month HbA1c data are available, an analysis of covariance (ANCOVA) will be performed at time of 6 month database lock and a MMRM at time of 12 month database lock.

In the protocol (1) Section 11.4.2, Analysis of primary efficacy endpoint(s), exploratory analysis for primary endpoint was modified. The Predictive Enrichment method is replaced by Subgroup Identification Based on Difference Effect Search (SIDES). The rationale is that the predictive enrichment procedure does not adjust for multiplicity. Additionally, the definition of subgroups is based on a score, defined as a function of multiple covariates, which makes difficult the clinical interpretation. On the other side, SIDES method uses fewer covariates (ie, 2 or 3 covariates), that is easier to interpret from a clinical point of view. Additionally, SIDES corrects for multiplicity.

As mentioned in Clinical Trial Protocol Amendment No. 01, an IA is planned when 1800 patients have completed their 6 month visit. The calculation takes into account one IA using a group sequential approach with an efficacy boundary based on a gamma (-3) alpha spending function.

The cut-off date for the IA is the date when 1800 patients have completed their 6 month visit.

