The information collected in the e-CRF on SU use, GLP-1 RA use and comorbidity at baseline slightly differs from the definition of randomization stratification factors as per IVRS, as detailed below in [Table 4](#).

Table 4 - Stratification factors discrepancies

	SU use	GLP-1 RA use	Comorbidity (used for HEDIS HbA1c target definition)
IVRS	"Used previously" (anytime in patient history)	"Used previously" (anytime in patient history)	Did the patient exhibit comorbid conditions as outlined per the IVRS worksheets? Refer to Protocol (1) Appendix G (anytime in patient history)
e-CRF	Currently being treated (at study entry)	Within past 6 months	Within past 12 months

IVRS = interactive voice response system; e-CRF = electronic case report form; GLP-1 = glucagon like peptide-1; HEDIS = healthcare effectiveness data and information set; RA = receptor agonist; HbA1c = glycosylated hemoglobin.

To assess the impact of these differences between IVRS randomization strata and the strata which can be derived based on e-CRF data, two sensitivity analyses will be performed.

1. SU use (y/n), GLP-1 RA use (y/n) as per e-CRF and the HEDIS target from IVRS will be used in the logistic regression model.
2. SU use (y/n), GLP-1 RA use (y/n) from IVRS included in the logistic regression model and HEDIS target strata will be dropped from the logistic model.

- **Sensitivity analysis of primary efficacy endpoint with MAR multiple imputation.**

As a sensitivity analysis to assess the impact of missing data, missing HbA1c data and documented (BG \leq 70 mg/dL) or severe hypoglycemia will be handled using the multiple imputation method.

Months 6 and 12 data will be imputed separately. For 6-months data, randomization strata, and treatment will be included in the imputation model. For 12-month data, 6-month data, randomization strata, and treatment will be included in the imputation model.

Documented hypoglycemia (yes/no/missing) and HbA1c values by visit will be presented by for each treatment group, using descriptive statistics.

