Patient characteristics on which potential subgroups will be defined, include randomization strata which are used in the primary efficacy analysis and other variables collected at baseline: randomization strata; SU use (y/n), GLP-1 RA use (y/n), baseline HbA1c (as continuous), baseline age, race/ethnicity, gender, baseline fasting glucose level, baseline BMI, duration of diabetes, diabetic disease history (diabetic retinopathy, diabetic sensory or motor

neuropathy, diabetic autonomic neuropathy, diabetic nephropathy), comorbidity (coronary artery bypass graft, percutaneous coronary intervention, ischemic vascular disease, thoracic aortic aneurysm, chronic heart failure, prior myocardial infarction, chronic renal failure or end stage of renal disease, dementia, blindness, and leg amputation). Since HbA1 target as per HEDIS depends on age and comorbidity, both already included, it will not be added to the list of covariates for subgroup search.

The global procedure includes the following steps:

- Balanced allocation procedure:

The data is split into one training data set on which the subgroup identification procedure will be applied, and one or several validation data set. This allocation procedure is based on an imbalanced score so that the distribution of patients' treatment and covariates is balanced between sets.

- SIDES recursive partitioning algorithm:

Subgroups are constructed from the training data set by recursively partitioning from covariates the data set into two subgroups at each parent group so that the treatment effect in one group is maximized compared to the other.

- Validation of identified candidates subgroups:

One validation set is used to confirm or reject candidate subgroups identified in the previous step based on-treatment effect p-value estimated on the validation set.

Note:

As specified in the article (6), the identification of candidate subgroups step can be applied to the entire data set, and confirmation performed in a subsequent independent study.

This will be the preferred option: the dataset will not be divided in training and test datasets, and only Step 2 (SIDES recursive partitioning algorithm) will be applied.

The SIDES recursive partitioning algorithm can be described as follows:

Consider the current parent subgroup. At the beginning, no covariate is used to define subgroup and the parent subgroup is the entire training set.

- Among covariates not already used to define parent subgroup,

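### The SIDES search omits the individualized HbA1c target on the ground that age and comorbidity stand in for it, but the search cannot form the <8% stratum from them; adding the target is a cheap, minor improvement

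*SAP*

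**What the plan says.** SAP 2.4.4.1 provides for SIDES only if superiority is not shown on the primary endpoint. Its candidate list is said to include the randomization strata used in the primary analysis, but one of these, the individualized HbA1c target, is then removed: "Since HbA1 target as per HEDIS depends on age and comorbidity, both already included, it will not be added to the list of covariates". The comorbidity entry is a list of named items, beginning "comorbidity (coronary artery bypass graft, percutaneous coronary intervention, ischemic vascular disease, thoracic aortic aneurysm, chronic heart failure, prior myocardial infarction" and continuing with renal failure, dementia, blindness and leg amputation, ten in all.

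The algorithm in the same section splits each parent on one further variable, "Among covariates not already used to define parent subgroup". It keeps the child with the larger effect from each split and stops at L covariates. L is called pre-defined but has no stated value. SAP 1.5 says that the "SIDES method uses fewer covariates (ie, 2 or 3 covariates".

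SAP 1.2.1 defines the target. It is <8% at age 65 or over, and also below 65 "and with evidence of any of these diseases/conditions"; it is <7% below 65 "and without evidence of any of these diseases/conditions listed above".

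Table 4 in SAP 2.4.4.1 adds that "The information collected in the e-CRF on SU use, GLP-1 RA use and comorbidity at baseline slightly differs from the definition of randomization stratification factors". For comorbidity, IVRS covers any time in the patient's history and the e-CRF covers the past 12 months.

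**The concern.** A variable can be a function of listed covariates and still be out of reach of a tree search that only intersects conditions. The omission would be harmless if SIDES could rebuild the target from age and comorbidity. If it cannot, a subgroup such as target <8% with no SU use can never be returned, and an effect that belongs to the target may be reported as an age effect.

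The target is one of four stratification factors and sets the threshold by which each patient counts as a responder. SIDES runs only after a failed primary test, and adding the target at that point would be a data-driven change, so the candidate list has to be right beforehand.

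**Working it through.** **Check of the planning inputs (SAP 1.3.1).** Comparator rates are 30.1 − 5.5 = 24.6% (target <7%) and 55.8 − 5.4 = 50.4% (target <8%). With a 70/30 mix, the overall rates are 0.7 × 30.1 + 0.3 × 55.8 = 37.81% and 0.7 × 24.6 + 0.3 × 50.4 = 32.34%. The usual two-proportion formula, n = [1.960√(2p̄q̄) + 1.282√(p₁q₁ + p₂q₂)]²/d² with d = 0.0547, gives 1598 per group, or 1634 with continuity correction. The plan states 1635, so the inputs reproduce it.

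**Can the search form each stratum?**

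- *Target <8%.* A SIDES subgroup is a set of conditions that must all hold. Requiring age 65 or over loses younger patients with a condition; requiring a younger age loses the older ones. Requiring a condition to be present loses older patients without it; requiring it to be absent loses patients who have it. Every added condition therefore removes some <8% patients, and with no condition the subgroup is everyone. Enumerating all AND combinations of 11 yes/no indicators (age 65 or over plus ten conditions) confirms that none equals this stratum. The same holds with a single any-comorbidity flag.
- *Target <7%.* This is age <65 and none of the conditions. Exactly one combination matches, and it uses all 11 indicators. With a single any-comorbidity flag it takes 2 splits, within the 2 or 3 mentioned in SAP 1.5.
- *With the target as a candidate.* Either stratum takes one split.

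**How good is age as a proxy?** Assume that 10% to 25% of patients are 65 or over and, as planned, 30% have target <8%. Age <65 is then 0.70/0.90 = 78% to 0.70/0.75 = 93% target-<7% patients. Age 65 or over captures 0.10/0.30 = 33% to 0.25/0.30 = 83% of the <8% stratum.

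**Illustration for the <8% stratum.** The following are assumptions, not document figures: a 10-point effect only in that stratum (50.4% against 60.4%), and a share b of all patients who are under 65 with a comorbidity. N = 3324, 1:1, Z = difference / √[(p₁q₁ + p₂q₂)/n per arm].

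Target <8%: n per arm = 0.30 × 1662 = 498.6; SE = √[(0.2500 + 0.2392)/498.6] = 0.0313; Z = 0.10/0.0313 = 3.19. For age 65 or over, n per arm = (0.30 − b) × 1662, so Z shrinks by √[(0.30 − b)/0.30].

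The SAP's splitting criterion is ρ = 2[1 − Φ((Z₁ − Z₂)/√2)], where a smaller value is a better split. A split on target has Z₂ = 0. A split at age 65 leaves some responders in the younger child, which raises Z₂.

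| Split | b | Share of <8% captured | Z₁ | Z₂ | ρ |
|---|---|---|---|---|---|
| Target | – | 100% | 3.19 | 0 | 0.024 |
| Age 65 | 5% | 83% | 2.91 | 0.38 | 0.073 |
| Age 65 | 10% | 67% | 2.61 | 0.71 | 0.18 |
| Age 65 | 15% | 50% | 2.26 | 1.02 | 0.38 |

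These ρ values are before the Sidak adjustment, which the SAP applies to covariates with more than two levels. Age would incur it unless dichotomized; a binary target would not.

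**Would the search run in this scenario?** The overall difference is 0.30 × 10 = 3.0 points (32.34% against 35.34%), with SE = √[(0.2188 + 0.2285)/1662] = 0.0164 and Z = 1.83. Against the critical value 1.995 (two-sided 0.046), and ignoring covariates and the interim, the primary test succeeds with probability Φ(1.83 − 1.995) ≈ 43%. SIDES would run in the remaining 57% or so.

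**The case against.** The strongest reply is that the target is not neglected. SAP 2.4.4.2 lists it as a subgroup factor for the primary endpoint, with a treatment interaction, forest plots and an analysis of each component, whether or not the primary test fails. SAP 2.4.5.1 does the same for hypoglycemia. This stands. A reader might infer that a target-specific effect would go unseen; for a one-way effect that is wrong, and an age subgroup from SIDES would be read beside the target result. The table above is itself a one-way comparison, so it shows how weak the proxy can be inside the search. It does not measure what the trial as a whole would miss.

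Four further points stand in part.

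- A reader might infer that neither stratum can be rebuilt. For <7% that depends on how comorbidity is coded. The SAP names ten conditions, but Table 4 treats comorbidity as one item, and one flag makes <7% reachable in two splits. For <8% the coding makes no difference.
- SIDES can return several candidates, and an age subgroup and a comorbidity subgroup together could cover the <8% stratum. Each would still be tested separately, never as the union.
- The e-CRF mismatch is conditional, because the SAP does not say which source supplies comorbidity to SIDES. Nor do the documents say how many patients have only a condition older than 12 months.
- The plan expects almost equal effects by target (5.5 and 5.4 points). The differing comparator rates (24.6% and 50.4%) show that target predicts response, not that it modifies the treatment effect. However, a search for unplanned heterogeneity need not assume the planned homogeneity.

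A scenario with 5.5 points only in target <7% adds little. The overall difference would be 0.70 × 5.5 = 3.85 points, with Z = 0.0385/√[(0.2188 + 0.2309)/1662] = 2.34. The primary test would then succeed about Φ(2.34 − 1.995) ≈ 63% of the time, and SIDES would not be run.

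**Conclusion.** The stated reason for the exclusion is wrong for this algorithm. That the <8% stratum cannot be formed follows from the SAP's own definitions and needs no numerical assumption. Whether the <7% stratum can be formed, and whether e-CRF comorbidity differs from the IVRS target inside the search, depend on coding and source choices that the SAP leaves open.

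The consequence is minor. It is confined to an exploratory search that runs only after a failed primary test and for which the SAP itself foresees confirmation in an independent study. No primary or secondary inference is affected. What is lost is mainly subgroups that combine target with another factor, together with the risk that a target effect is returned under an age label. The fall in Z from 3.19 to between 2.91 and 2.26 is an illustration that rests on the assumed 10-point effect and b of 5% to 15%; no figure is available for the loss in combined subgroups.

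**What to change.** Add the IVRS individualized HbA1c target (<8%/<7%) to the SIDES candidate covariates as a binary variable, and delete the sentence that excludes it. Age and the comorbidities stay in the list. Make the change before treatment-level results are known. In the same edit, it would help to state whether comorbidity enters as ten items or one flag, which source supplies it, and the value of L.

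The cost is one SAP sentence, one more binary candidate in the resampling adjustment, and some redundancy with age.
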